3 OBJECTIVES AND ENDPOINTS

OBJECTIVES	ENDPOINTS	JUSTIFICATION FOR ENDPOINTS
Primary		
 To determine if patient postoperative outcomes, measured by the Knee Society Score, are improved by using the X4 brace with the Motion Intelligence platform To monitor the study group for any device related adverse events 	 To compare the Knee Society Scores, both objective and subjective scores, done preoperatively and at 8 weeks postoperatively between the control and study groups To monitor the study group for any device related adverse events 	The Knee Society Score is a validated tool used for assessing outcome in total arthroplasty patients Patients will be followed to ensure there are no issues with the utilization of the X4 brace
Secondary		
 To determine if there is a reduction in the rehabilitation costs (inpatient or outpatient) by using the X4 brace with the Motion Intelligence platform 	 To compare the number of inpatient days in a rehabilitation center between the control and study groups To compare the number of outpatient visits to a physical therapy center between the control and study groups 	To evaluate if the X4 brace provides user- friendly, cost-effective, enhanced patient recovery following total knee arthroplasty
 To evaluate patients satisfaction with the X4 brace with the Motion Intelligence platform 	 To evaluate patient's satisfaction with the X4 brace with the Motion Intelligence platform via the "System Usability Scale" (SUS) questionnaire (study group only) 	
 To evaluate patients compliance and adherence using the X4 brace with the Motion Intelligence platform 	• To measure patient's compliance using the X4 brace with the Motion Intelligence platform by counting how many days they used the platform as prescribed within an 8 week period. A patient will be	

OBJECTIVES	ENDPOINTS	JUSTIFICATION FOR
		ENDPOINTS
	considered compliant if they use the platform once a day.	
	 To measure patient's adherence using the X4 brace with the Motion Intelligence platform. Adherence is defined as performing the entire exercise routine as prescribed once a day. 	
 To evaluate provider satisfaction using the X4 brace with the Motion Intelligence platform 	 To evaluate provider satisfaction with the X4 brace with the Motion Intelligence platform via the "System Usability Scale" (SUS) questionnaire (study group only) 	In order for this technology to become part a postoperative regime the platform should be both effective and user friendly for the provider

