6 STUDY INTERVENTION

6.1 STUDY INTERVENTION(S) ADMINISTRATION

6.1.1 STUDY INTERVENTION DESCRIPTION

Patients will be consented for the study at any time during the preoperative period. Following the surgical procedure the inclusion/exclusion criteria will be confirmed. Patients meeting study inclusion/exclusion will be randomized via the REDCap system when their discharge location (home vs inpatient rehabilitation) has been confirmed. Patients randomized to the X4 brace arm of the study will be assisted with downloading the Motion Performance Platform and provided with the X4 brace during their hospital stay. The average length of stay in the hospital is 2 days. During the hospital stay the study team will work with the patient and family members to insure they are adequately trained in the use of the device and comfortable using the platform. Contact information will be provided for any issues or concerns.

PROCESS AND PATIENT ON-BOARDING

POST-OPERATIVE FOLLOWING RANDOMIZATION

Following randomization the patient will be shown how to apply brace and assisted in downloading the Motion Intelligence application from either the Apple iStore or Google Play. The patient will be assisted with pairing the device to the brace. The patient will be instructed on how to use the application and importance of using the application.

The patient will be educated to do their exercises twice a day, once in the morning and once in the afternoon. Additionally, the application screen will monitor their progress post-surgery by showing them how many steps they have taken in a day, their active time and average flexion and extension. If the patient would like to be reminded that they need to do their exercises, they can set up a reminder by going to the "Settings".

Exercise Program:

The Exercise program was developed by some Key Opinion Leaders based on common practice. The investigators have reviewed the program and are in agreement with this program. These exercises are completed throughout the 56 day program and are selected for predetermined time periods (days) after surgery (see exercise regime for details on timing):

- 1. Ankle Pumps / Ankle Circles
- 2. Isometric Quad Sets
- 3. Supine Heel Slides
- 4. Straight leg raise
- 5. Hamstring and Calf Stretch * Hold 10 Seconds*
- 6. Clamshells
- 7. Seated Heel Slides in Chair
- Seated Passive Knee Extension *Hold 30 Seconds*

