Each exercise has a video to show the patient how to complete the exercises. The patient starts the exercise session by selecting the first exercise. They watch the video on how to perform the exercise. Once the exercise is completed they select "Done" and move to the next exercise. The exercises must be done in order, however, if the patient cannot complete the exercise they can select "skip" and give a reason for the skip. Any exercise that bends the knee will show up on the screen when it is performed. Each period the patient has a target range of motion goal for both flexion and extension and a pain goal. The patient can see their progress while doing the exercises. Progress is based on color: with Green indicating the patient has reached the target. Yellow and Red indicate that the target has not been reached. At the end of the session the patient will be asked about their pain level and will record their highest amount of range of motion (ROM) and then they have a timer for 20 minutes of icing.

Exercise Regimen:

Postoperative Day (POD)	0-6		
Range of Motion Flexion - Target	80		
Range of Motion Extension - Target	15		
Pain - Target	7		
	Reps	Sets	Time/Day
Ankle Pumps / Ankle Circles	10	1	2
Isometric Quad Sets	10	1	2
Supine Heel Slides	10	1	2
Straight leg raise			
Hamstring and Calf Stretch * Hold 10 Seconds*			
Clamshells			
Seated Heel Slides in Chair	10	1	2
Seated Passive Knee Extension *Hold 30 Seconds*	10	1	2

	7-		
Postoperative Day (POD)	13		
Range of Motion Flexion - Target	90		
Range of Motion Extension - Target	10		
Pain - Target	6		
	Ren	Set	Time/Da
	s	s	y y
Ankle Pumps / Ankle Circles	s 10	s 1	y 2
Ankle Pumps / Ankle Circles Isometric Quad Sets	s 10 10	s 1 1	y 2 2
Ankle Pumps / Ankle Circles Isometric Quad Sets Supine Heel Slides	s 10 10 10	s 1 1 1	y 2 2 2 2

Hamstring and Calf Stretch * Hold 10 Seconds*

Clamshells

Seated Heel Slides in Chair	10	1	2
Seated Passive Knee Extension *Hold 30 Seconds*	10	1	2

Postoperative Day (POD)	14-20		
Range of Motion Flexion - Target	100		
Range of Motion Extension - Target	5		
Pain - Target	6		
	Reps	Sets	Time/Day
Ankle Pumps / Ankle Circles	10	1	2
Isometric Quad Sets	10	1	2
Supine Heel Slides	10	1	2
Straight leg raise			
Hamstring and Calf Stretch * Hold 10 Seconds*			
Clamshells			
Seated Heel Slides in Chair	10	1	2
Seated Passive Knee Extension *Hold 30 Seconds*	10	1	2

Postoperative Day (POD)	21-27		
Range of Motion Flexion - Target	105		
Range of Motion Extension - Target	0		
Pain - Target	5		

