9 STATISTICAL CONSIDERATIONS

9.1 STATISTICAL HYPOTHESES

• Primary Efficacy Endpoint(s):

Knee Society Scores will be obtained prior to surgery, and at 8 weeks postoperatively

- Objective knee score (completed by the surgeon)
- Subjective knee score (completed by patient)
- Secondary Efficacy Endpoint(s):

All outcomes will be measured at 8 week postoperative visit or the visit closest to this time point

Outcomes for all patients regardless of discharge location

• Number of outpatient visits to a physical therapy center

Outcomes for patients discharged to inpatient rehabilitation

o Number of inpatient days in a rehabilitation center

Outcomes for patients randomized to the X4 brace with the Motion Intelligence platform

- Patient satisfaction with the X4 brace with the Motion Intelligence platform: Patients will complete the System Usability Scale (SUS)
- Compliance in using the X4 brace with the Motion Intelligence platform: Patients will be instructed to use the X4 brace twice a day. For each day, a subject will be considered compliant if they access the platform at least once a day, and non-compliant if they do not access at all the platform that day.
- Adherence using the X4 brace with the Motion Intelligence platform: For each day, a subject will be considered adherent if they perform the entire exercise routine as prescribed at least once a day, and non-adherent if they do not perform the entire exercise routine that day.
- Primary Safety Endpoint(s)
- Adverse Events related to the X4 brace will be collected in patients regardless of discharge location.

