9.4.3 ANALYSIS OF THE SECONDARY ENDPOINT(S)

Secondary Outcomes: Efficacy

Outcomes for all patients regardless of discharge location:

The association between number of outpatient visits to a physical therapy center and intervention group will be examined using Poisson regression. Discharge location (home, inpatient rehabilitation) will also

be included in the model. If the interaction between intervention group and discharge location is significant, then pairwise comparisons of intervention group within each discharge location will be examined within the Poisson regression model. If the Poisson model does not fit the data well, alternative methods for count data will be considered.

Outcomes for patients discharged to inpatient rehabilitation:

Number of inpatient days in a rehabilitation center

The association between number of inpatient days in a rehabilitation center and intervention group will be examined using Poisson regression. If the Poisson model does not fit the data well, alternative methods for count data will be considered.

Outcomes for patients randomized to the X4 brace with the Motion Intelligence platform:

The association between patient satisfaction with the X4 brace, as measured by the SUS scale, and discharge location (home, inpatient rehabilitation) will be examined using the two sided, two sample t-test. If the usual assumptions required for the t-test are not met, either a suitable transformation, or an appropriate nonparametric method will be used.

The association between number of days of compliance and discharge location will be examined using Poisson regression. If the Poisson model does not fit the data well, alternative methods for count data will be considered.

The association between number of days of adherence and discharge location will be examined using Poisson regression. If the Poisson model does not fit the data well, alternative methods for count data will be considered.

Other outcomes:

Provider satisfaction with the X4 brace, as measured by the SUS scale will be described by calculating summary statistics (median, 25th percentile, 75th percentile, minimum and maximum).

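### Compliance and adherence are compared by discharge location as raw day counts with no defined window or denominator, so unequal days of access could be read as unequal use

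*Combined protocol and SAP*

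**What the plan says.** Section 3 (and the synopsis) measures compliance "by counting how many days they used the platform as prescribed within an 8 week period". Section 9.1 supplies the daily rules: a patient is "non-compliant if they do not access at all the platform that day", and "non-adherent if they do not perform the entire exercise routine that day". Neither section names the first countable day or exempts days before the patient has the platform.

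Section 6.1.1 says "These exercises are completed throughout the 56 day program". Its regimen tables begin with a block for POD 0 to 6 and end at POD 56, which is 57 calendar days. The same section says that patients "will be randomized via the REDCap system when their discharge location (home vs inpatient rehabilitation) has been confirmed". The brace is supplied and training given after that, during the hospital stay, which averages 2 days. Section 6.3 also makes the assignment available only once the destination is known. The schedule of activities (1.3) puts randomization and device education between POD 1 and discharge.

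Section 9.4.3 gives the analysis: "The association between number of days of compliance and discharge location will be examined using Poisson regression". Adherence is handled the same way. No offset is stated for either. The fallback is another method for count data if the Poisson model fits poorly.

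The end of the count is also loose. Section 9.1 measures secondary outcomes at the 8-week visit or whichever visit is nearest, while the regimen tables and the daily log stop at POD 56.

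**The concern.** A day on which the patient has no platform cannot be a compliant or adherent day. Handover waits for the discharge location to be confirmed, and discharge location is the factor that section 9.4.3 then tests. If one destination takes longer to confirm, or one group's nearest visit falls later, that group has a different number of scorable days. A raw count would show this as different use even if daily behaviour were identical.

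This comparison is the only planned test of either endpoint. The fallback does not help, because it responds to poor model fit and not to unequal opportunity. The plan does not name the handover date among the data to be recorded, so the problem might not be checkable afterwards. Section 8.3.1 starts the adverse-event period when the patient begins using the brace, but that clock is not carried over to the day counts.

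**Working it through.** **The plan's own figure.** The documents give no figure for these two endpoints. The one sample-size figure, 120 per group, is for the subjective Knee Society Score and reproduces: a difference of 10, SD 27.5, two-sided 0.05 and 80% power give 119 per group by the normal formula and 119.7 by the t-test. It matters here only because it sets 120 X4 patients.

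**Expected count.** Let W be the programme days (56 or 57), d the days before handover and c the true share of available days used. The expected count is c × (W − d).

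- Loss with d = 1: 1/57 = 1.8%. With d = 2: 2/57 = 3.5%, or 2/56 = 3.6%.
- With equal c, the inpatient/home ratio is (W − d_inpatient)/(W − d_home). For W = 57:
  - 2 against 2 days: 55/55 = 1.000
  - 2 against 3 days: 54/55 = 0.982
  - 2 against 4 days: 53/55 = 0.964
- Dividing each count by its own W − d gives a ratio of c/c = 1.00 whatever the handover days.

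**False differences.** Section 2.1 puts transfer to rehabilitation at about 41%. Applied to 120 X4 patients this is about 49 inpatient and 71 home; that the trial matches it is an assumption. True use is set equal in both locations, with binomial days out of 56 at home and 56 minus the gap for inpatients. The log ratio of means is tested at two-sided 0.05, with at least 4,000 simulated trials per setting. Mean daily use is 80%; the between-patient SD is √(0.8 × 0.2/11) = 0.12 for beta(8,2) and √(0.8 × 0.2/41) = 0.06 for beta(32,8). The use patterns and the gaps are assumptions.

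| Use pattern (both locations), empirical standard errors | No gap | 1 day | 2 days |
|---|---|---|---|
| beta(8,2) | 5% | 9% | 22% |
| beta(8,2) plus 5% never-users | 5% | 5% | 9% |
| beta(8,2) plus 10% never-users | 5% | 5% | 7% |
| beta(32,8), little variation | 5% | 16% | 48% |

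Analysing days out of available days, with empirical standard errors, held the rate near 5% at every gap.

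Plain Poisson standard errors behave differently:
- beta(8,2): about 7%, 12% and 27%.
- beta(32,8): about 0.4%, 3% and 16%.
- With 5% or 10% never-users they already reject in about 28% or 41% of trials with no gap. That is a separate dispersion problem, and it is why the fix asks for robust standard errors.

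**How large can the handover gap be?** Assume that the 2-day average stay applies to trial patients, that 59% go home with a mean stay of at least 1 day, and that handover is as late as discharge. Then the inpatient mean is at most (2 − 0.59 × 1)/0.41 = 3.4 days, and the gap at most 3.4 − 1 = 2.4 days. This bounds the start of the count only; the documents do not bound a difference in its end.

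**The case against.** The strongest reply is that nothing in the documents shows handover to be later for either destination. That is correct. A reader might infer that the comparison is biased as planned, but a delay shared by both locations leaves the ratio at 1.00, so the bias is conditional.

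Three other strong readings also go too far:

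- **Every X4 patient loses POD 0.** This needs the count to start at POD 0. The regimen table starts there, but the endpoint only refers to 8 weeks, and the schedule of activities appears to start the exercise programme at discharge.
- **The count understates use.** A count of days used is accurate as a count. It understates use only if divided by 56 or 57, and the plan does not do that.
- **A 3-day handover gap is realistic.** It would give false differences in about 44% of trials (beta(8,2), empirical standard errors), but it exceeds the 2.4-day limit above. Since training takes place before discharge, even 2 days is near the extreme.

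It is also fair to say that this is a non-randomized comparison within one arm, on secondary endpoints, and that a 1-day gap does almost nothing once some patients never use the device. These points limit the size. They do not answer the undefined window or the missing denominator.

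**Conclusion.** The point holds in conditional form. The counting window has no stated start and no settled end, days of access vary by patient, and the planned model has no term for that. The home-versus-inpatient comparison could be biased if handover timing or the end of the count differs by location; the documents do not say that either does.

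The likely loss of countable days is 1 to 2 of 56 or 57. A gap of 1 to 2 days would give a false difference in about 5 to 22% of trials under most of the assumed use patterns, and in up to about 48% if use varies little between patients. These rates rest on the assumed 71/49 split, 80% mean use, assumed variation and empirical standard errors. The Knee Society Score analyses and the comparisons between randomized arms are not affected. The change is worth making because it costs almost nothing.

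**What to change.** In section 9.1, define the first countable day as the day after platform training is completed and the last as POD 56, for every X4 patient, including those who stop using the brace but stay in the study. With training on POD T, available days are 56 − T: 55 if T = 1, 54 if T = 2. Record the training and handover date in REDCap. Reconcile the 56-day description with tables that span 57 days, so that the denominator is unambiguous.

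In section 9.4.3, analyse compliant and adherent days out of the days available in that window. Use either a grouped binomial model with robust standard errors, or a count model with log available days as offset and robust standard errors. Report the mean share of available days by location. Defining the start alone is not enough: with a fixed end, later handover still leaves fewer possible days, so the denominator is needed too.

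The cost is a few sentences and one date field. Results become a share of available days instead of a simple count. No treatment, visit or sample size changes.

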9.2 SAMPLE SIZE DETERMINATION

Sample Size Justification:

Based on preliminary data (from the Total Knee Arthroplasty Registry), there were 244 patients treated under the standard of care, with a KSS subjective score obtained between 6 and 10 weeks after surgery. We will use this information to estimate the KSS subjective score for the standard of care group at 8 weeks after surgery. The mean KSS subjective score in these patients was 108.5, with a standard deviation of 27.5. We believe that a 10 point improvement is clinically meaningful. We further assume that the scores for those discharged to home, and those discharged to inpatient rehabilitation will be similar, (i.e. no interaction between intervention group and discharge location). Therefore, we will use a two sided two-sample t-test to simplify the calculation. In addition, the KSS subjective scores in our preliminary data were normally distributed, and so the calculation uses the raw (untransformed) data.

A sample size of 120 patients per group will yield 80% power to detect a 10 point difference between the two intervention groups using a two sided two-sample t-test at the 0.05 significance level. As

dropout is expected to be very low, no adjustment for attrition will be made. Therefore, the total sample size will be 240 patients (120 per group).

9.3 POPULATIONS FOR ANALYSES

Intention to Treat (ITT):

All analyses will be carried out according the ITT principle. The ITT population will be all patients randomized, regardless of whether or not treatment was administered. All patients will be analyzed in the group to which they were randomized.

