7 STUDY INTERVENTION DISCONTINUATION AND PARTICIPANT DISCONTINUATION/WITHDRAWAL

7.1 DISCONTINUATION OF STUDY INTERVENTION

Patients may discontinue using the X4 brace, however, this does not mean discontinuation from the study. The brace is single use and patients will not be required to return the brace.

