8.3 ADVERSE EVENTS AND SERIOUS ADVERSE EVENTS

8.3.1 DEFINITION OF ADVERSE EVENTS (AE)

Medical Device Reporting:

This clinical trial is evaluating a commercially available marketed medical device (X4 brace). The device is being used according to the manufacture's guidelines.

This study will adhere to the adverse event reporting regulations of the Centers for Devices and Radiological Health (CDRH), part of the Food and Drug Administration (FDA) regulations. In accordance with the Safe Medical Devices Act of 1990 (SMDA) (Public Law 102-629) (21 CFR 803.32 (c)) ambulatory surgery centers, hospitals, outpatient diagnostic centers and other user facilities are required to report all incidents in which a medical device or user error may have caused or contributed to the death, serious injury or serious illness of a patient.

Adverse Event Reporting Period

The study period during which adverse events must be reported is defined as the period from the initiation of any study procedures to the end of the study treatment follow-up. For this study, the initiation of study procedure will be from when the study subject starts using the X4 brace with the Motion Intelligence platform through the 8 week postoperative visit.

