9.4.4 SAFETY ANALYSES

Safety Outcomes:

Outcomes for patients randomized to the X4 brace regardless of discharge location

- Adverse events: Each subject will be categorized at the end of the study as having had one or more adverse events, or not having had any adverse events.
- Serious adverse events: Each subject will be categorized at the end of the study as having had one or more adverse events, or not having had any serious adverse events.

Not Applicable

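### With ITT as the only analysis set, X4 patients who never use the brace enter the device-related adverse event denominator although they cannot have such an event

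*Combined protocol and SAP*

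**What the plan says.** Section 9.3 sets one rule for the whole trial: "All analyses will be carried out according the ITT principle". It then defines the set: "The ITT population will be all patients randomized, regardless of whether or not treatment was administered". Section 7.2 repeats both statements. No safety, treated or exposed population is defined anywhere.

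Section 9.4.4 gives the group for the safety analysis as "Outcomes for patients randomized to the X4 brace regardless of discharge location". Within it, "Each subject will be categorized at the end of the study as having had one or more adverse events, or not having had any adverse" (quote cut before its final word). There are two categories, and none for patients who were never exposed.

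Section 9.1 states the primary safety endpoint: "Adverse Events related to the X4 brace will be collected in patients regardless of discharge location". Section 8.3.1 defines the reporting period as running "from when the study subject starts using the X4 brace with the Motion Intelligence platform through the 8 week postoperative visit".

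**The concern.** ITT protects a randomized comparison from selection after randomization. The safety analysis contains no such comparison: section 9.4.4 describes the X4 arm alone, and section 8.3.5 says that no study-related events will occur in controls. Including unexposed patients therefore protects nothing.

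It does lower the result, and always in the same direction. An X4 patient who never uses the brace has no reporting period under section 8.3.1 and cannot have an event caused by the brace, but is still counted among those without one. The lower the uptake, the safer the device appears. Device-related adverse events are listed as a primary endpoint beside the Knee Society Score, so the denominator should be fixed before data are seen.

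**Working it through.** **Inputs from the documents**
- Planned X4 arm: 120 patients (section 9.2). The figure reproduces. For a 10-point difference, SD 27.5, two-sided alpha 0.05 and 80% power, the exact t-test calculation gives 120 per group with power 0.801.
- Denominator: all patients randomized to X4 (sections 9.3 and 9.4.4).
- Start of reporting: first use of the brace (section 8.3.1).

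**Inputs that are assumed**
- f, the fraction of the X4 arm that never uses the brace. The documents give no value, so 2%, 5%, 10% and 20% are shown.
- The number of device-related events. None is projected, so 5 and 0 serve as examples.

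**Formula.** Let p be the proportion of brace users with a device-related event. Users number 120 × (1 - f), and never-users contribute no such events. Hence

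proportion over all randomized to X4 = p × 120 × (1 - f) / 120 = p × (1 - f).

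The relative shortfall equals f, whatever p is.

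**Results.** The number of users is rounded to a whole patient; at f = 2%, 120 × 0.98 = 117.6, taken as 118. With no events, the upper limit of the exact two-sided 95% interval on n patients is 1 - 0.025^(1/n).

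| f (assumed) | Users | 5 events | Upper limit, 0 events |
|---|---|---|---|
| 0% (ITT figure) | 120 | 5/120 = 4.17% | 3.03% |
| 2% | 118 | 5/118 = 4.24% | 3.08% |
| 5% | 114 | 5/114 = 4.39% | 3.18% |
| 10% | 108 | 5/108 = 4.63% | 3.36% |
| 20% | 96 | 5/96 = 5.21% | 3.77% |

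For scale, the exact 95% interval for 5/120 runs from 1.4% to 9.5%. Every shift in the table is small beside that width. The difference is that the shift has a fixed direction and can be removed.

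**The case against.** **Never-use should be rare.** Under sections 6.1.1 and 6.3, randomization takes place after surgery, once eligibility is confirmed and the discharge location is known. X4 patients then receive the brace, are shown how to apply it and are helped to install and pair the app while in hospital. A smartphone is an entry criterion (section 5.1), and patients who are silent for more than 72 hours are contacted (section 6.4). This stands. It makes values of f near 20% unlikely and limits the size of the point, but it does not make the denominator right.

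**Some never-users could still have an adverse event recorded.** A reader might infer that such patients are event-free for every kind of adverse event. The documents do not support that. Section 8.3.4 asks for all events on study to be documented whatever their relationship to the device, in tension with sections 8.3.1, 8.3.3.1 and 8.3.5. Under section 8.3.4 a never-user could have an any-cause event, though not a brace-related one, so the point is confined to device-related events.

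**Patients who stop early.** Section 7.1 says "Patients may discontinue using the X4 brace, however, this does not mean discontinuation from the study", and a reader might conclude that early stoppers dilute the figure in the same way. They do not: they were exposed and can have device-related events. They belong in a safety set defined by at least one use, so the choice between ITT and a treated set leaves them where they are.

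**No rate is actually named.** Section 9.4.4 sorts subjects into two groups and specifies neither a proportion nor an interval, and no test or stopping rule depends on one. That is correct; the proportion discussed here is the one the classification implies. It is a further reason to write down both the denominator and the summary.

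**Low use will be visible anyway.** Compliance days are a secondary outcome in the X4 arm, so non-use will appear there. This helps a careful reader but does not correct the safety figure.

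**Conclusion.** The point holds for device-related events. As written, the plan places X4 patients who never use the brace in the denominator of the primary safety endpoint, and the implied proportion is (1 - f) times the proportion among users. The direction is certain whenever f is above zero and device-related events occur.

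The size is not known, because it rests on an f that the documents do not give. If f is 2%, the shift in the five-event example is under a tenth of a percentage point; if f is 20%, it is about one point. In-hospital supply and training make the lower end more plausible. A reader might take the 20% row as a forecast of poor uptake, but nothing in the documents supports that; it only marks the end of the assumed range. The sample size and the ITT efficacy analyses are not affected.

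**What to change.** In section 9.3, define a safety population: patients randomized to X4 who put the brace on at least once. Establish this from the hospital fitting record or from any sensor or app record, whichever shows use. Sensor data alone should not decide membership, because a patient whose device failed could be dropped, and section 8.3.2 lists device failure and malfunction among the ways a device may contribute to harm.

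In section 9.4.4, use this population as the denominator for the device-related AE and SAE proportions, each with an exact 95% confidence interval, and report how many X4 patients never used the brace. Keep ITT for the efficacy analyses.

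The cost is a few sentences in two sections. The protocol describes in-hospital fitting but names no data field for it, so one REDCap item recording first application may be needed. No change to sample size or visits follows. If every X4 patient uses the brace, the two denominators coincide; otherwise the reported safety figure may be slightly less favourable.
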